To determine the effect of live and pre-recorded music therapy on vital variables in newborns older than 32 weeks hospitalized in the Neonatal Intensive Care Unit of the Clinica Universitaria Colombia (CUC).

Secondary objectives

- To describe the demographic and clinical characteristics of study participants.
- To analyze the effect of live and pre-recorded music therapy on the vital signs (heart rate, respiratory rate, and oxygen saturation) of study participants.
- To categorize the stressful events, present in neonatal intensive care units according to their origin, namely auditory, tactile, and visual.

Methodology

Study Design

A prospective analytical, pragmatic clinical trial-type study will be conducted to provide evidence on the benefits of health interventions in real-world settings (in routine clinical practice). The study will be conducted at the Neonatal Intensive Care Unit of the CUC in Bogotá D.C. during the period from May 1st to June 30th, 2024.

Study Population

The study will include newborns who are older than 32 weeks gestational age at birth and who are hospitalized in the Neonatal Intensive Care Unit of the CUC.

Inclusion criteria

All newborns who meet the following inclusion criteria will be included:

- Gestational age at birth greater than or equal to 32 weeks.
- Birth weight greater than or equal to 1500 grams.
- Be at least 72 hours of postnatal age.

Exclusion criteria

All newborns who meet at least one of the following criteria will be excluded:

- Respiratory disturbances in the last 48 hours such as:
 - o Apnea or Brief Resolved Unexplained Events (BRUE).
 - o Need for invasive mechanical ventilation.
- Hemodynamic alterations in the last 48 hours such as:
 - o Hypotension (systolic, diastolic, or mean BP < P5) or hypertension (systolic, diastolic, or mean BP > P95).
 - o Bradycardia (HR < 100/min).
 - o Shock of any etiology
 - o Requirement for volume expanders, infusion of inotropic, vasodilators and/or prostaglandin E1
- Neurological alterations such as:
 - o Perinatal asphyxia at birth manifested by the need for resuscitation, APGAR < 3 at 5 minutes and/or ≤ 5 at 10 minutes, and metabolic acidosis in cord gases with pH < 7 and BE < -12.
 - o Hypoxic-ischemic encephalopathy.
 - o Seizure syndrome for up to 48 hours after the last clinical event or alteration of the brain pattern.
 - o Interventricular hemorrhage in preterm infants in the first week of diagnosis.

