Heart rate	Number of heartbeats measured at minute 0, from minute 0 to 30 minutes after the procedure continuously and 30 minutes after the intervention.	Quantitative – Discrete	Beats per minute (bpm)
Respiratory rate	Number of breaths measured at minute 0, from minute 0 to 30 minutes after the intervention continuously and at 30 minutes after the intervention.	Quantitative – Discrete	Breaths Per Minute (rpm)
Oxygen saturation	Measurement of the percentage of oxygen availability in the blood, measured at minute 0, from minute 0 to 30 minutes after the intervention continuously and at 30 minutes after the intervention.	Quantitative – Discrete	Percentage of SaO ₂ (SaO ₂ %)

Description of interventions

Music therapy is a non-pharmacological therapeutic intervention that will be implemented through two modalities: live and pre-recorded music. Group A will be comprised of patients who have been exposed to live music, which will be carried out by a music therapist using the guitar as the only musical instrument. Instrumental lullabies will be used, which will be selected by the patients' legal guardians. Group B corresponds to patients who will be exposed to pre-recorded music, of the genre of lullabies, instrumental type, using a speaker that will be placed inside the patient's incubator. Group C will be those patients in whom no musical intervention will be performed.

The patient will be placed in an incubator, monitored with a vital sign monitor and pulse oximetry, and under the supervision of a research assistant. The research assistant will be responsible for recording the variables at minute 0, from minute 0 to minute 10, and 30 minutes after the completion of music therapy or non-intervention. The volume will be controlled in the three groups by means of a decibel regulator, with a maximum volume of 70 dB.

During the intervention and for a period of 30 minutes following its conclusion, singing will be prohibited by the music therapist or, in the case of groups A and B, by the parents. This prohibition will be implemented in the same manner in group C, which will be devoid of any form of music exposure in order to prevent the introduction of confounding variables. Both live and pre-recorded music will be instrumental in nature, lacking any lyrics. In accordance with the protocol for admission to the neonatal unit, the use of electronic devices is restricted. Consequently, patients will not be exposed to auditory stimuli of this nature.

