Sources of information

The source of information will be primary. Demographic and clinical data will be obtained from the medical record. The vital signs data such as heart rate, respiratory rate and oxygen saturation will be obtained from the records of the monitors of the intensive care units, at the established times, which are: at minute 0, from minute 0 to minute 10 continuously and at 30 minutes after the intervention.

Standardization of measurements

For the standardization of measurements of the different physiological variables, several elements will be considered. First, the trademark of the medical equipment manufacturer of each of the tools that will be used (vital sign monitor and pulse oximeter) will be verified, verifying that they correspond to the same commercial brand since they are different brands, there may be variability between the standard calibration measurements considered within the critical range. Second, it will be verified that each medical tool used has been calibrated in the last 6 months, recording the date of last calibration so that the device can be used during the study.

Subsequently, the professional in charge of the music company will verify that the guitar to be used during the live music is in tune and suitable for use. A decibel regulator will be used during the implementation of the pre-recorded and live music, which will adjust the volume of the sound emitted. to ensure the same decibels per research subject, with a maximum allowable of 70 dB. Vital variables will be recorded at minute 0, from minute 0 to minute 10 and at 30 minutes after the intervention.

Primary Outcome

The primary outcome of this study is the heart rate (HR), which will be measured through pulse oximetry every minute, beginning at minute 0 (prior to the intervention), then from minute 0 to minute 30 (during the intervention), and finally at 30 minutes after the intervention.

Secondary Outcomes

- Respiratory rate (RR) will be measured through pulse oximetry every minute, beginning at minute 0 (prior to the intervention), then from minute 0 to minute 30 (during the intervention), and finally at 30 minutes after the intervention.
- Oxygen saturation (SO) will be measured through pulse oximetry every minute, beginning at minute 0 (prior to the intervention), then from minute 0 to minute 30 (during the intervention), and finally at 30 minutes after the intervention.

Analysis of information

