In accordance with the provisions of Resolution 8430 of 1993 (26) of Colombia, as the population of this study is minors, who in this case are newborns who, due to their neurocognitive development, cannot exercise the principle of autonomy *per se*, this will be delegated to their guardian or legal representative through the completion of informed consent. The objectives and methodology of the research will be clearly explained to the legal representative of the neonate, including the type of music to be used, the daily duration of each session, the time of exposure, and the data to be collected. Conversely, the legally appointed representative will be permitted to observe the child's participation in the study as it progresses, provided that this does not result in any direct alteration of the results through manipulation or direct contact with the patient. This is to ensure that the principle of autonomy is not violated. Furthermore, the legal representative of the newborn will have the option to withdraw from the study at any time, without affecting the medical care of the newborn. This study is classified as a research study with a higher than minimum risk because the intervention can modify the physiological variables of the newborn. However, based on previous studies conducted nationally and internationally, it can be determined that the use of music therapy is at least as safe and advantageous, in light of the foreseeable risks and benefits, as any other established effective alternative.

In order to guarantee the privacy and confidentiality of the information of the subjects involved in the study, the provisions of the Habeas Data Law (Law 1581 of 2012) and Resolution 1995 of 1999 will be taken into account. An alphanumeric code will be used to identify the study subjects. Only the researchers will have access to the databases, and the data will be safeguarded for up to one year after the publication of the results. No sensitive information will be disclosed in the publication or in other

documents drafted during the investigation. The results of this research will only be used to provide new knowledge and encourage new studies.

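### A trial that rates itself above minimum risk prespecifies no uniform capture, by arm, of apnea or of an interrupted session and its reason

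*Protocol*

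**What the plan says.** **Risk and withdrawal.** Ethical Considerations rates the study as "higher than minimum risk because the intervention can modify the physiological variables of the newborn". It also provides that "the legal representative of the newborn will have the option to withdraw from the study at any time". On the basis of previous studies, it then judges that "the use of music therapy is at least as safe and advantageous" when set against established alternatives.

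**What is collected.** The Variable Matrix lists demographic, birth, comorbidity, history, visit and singing items. Its only measurements during the study are heart rate, respiratory rate and oxygen saturation. Primary Outcome and Secondary Outcomes name the same three, each taken every minute from minute 0 to 30 and again 30 minutes after the intervention. Analysis of information tests these variables and defines no event.

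**Where apnea appears.** It is mentioned in the Background as a consequence of NICU noise, and in Exclusion criteria as a reason not to enter if it occurred in the last 48 hours. It is not an on-study item.

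**Who records.** Under Description of interventions, each infant is "under the supervision of a research assistant", who is responsible for "recording the variables at minute 0, from minute 0 to minute 10, and 30 minutes after the completion of music therapy or non-intervention". Standardization of measurements repeats the shorter window: "Vital variables will be recorded at minute 0, from minute 0 to minute 10 and at 30 minutes after the intervention".

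**The concern.** The protocol accepts that the intervention may disturb the infant and foresees that a guardian may end participation. It also regards apnea as serious enough to bar entry. Two things that a reader of the trial report would want to know are how many infants in each arm had an apnea and how many sessions were cut short, and why. Neither has a place on the planned record.

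This differs from a table left for later. The protocol itself fixes what is collected, and an analysis plan can tabulate only what was captured. A reason for stopping that nobody wrote down cannot be recreated.

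The gap also touches interpretation. If music stops early and the monitor runs on, the infant may look like one with a full session. If recording stops as well, the gap looks like any other missing reading. In arms of 15, a few such infants matter.

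**Working it through.** The protocol has no event figure to reproduce. The only planned number used is the Sample size section's 45 infants allocated 1:1:1, so 45/3 = 15 per arm and 30 in the two music arms together.

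**1. Could the planned items stand in for the missing ones?**

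- *Bradycardia and desaturation:* yes, they can be derived later from the minute readings. They are not part of this point.
- *Apnea:* only respiratory rate comes close (see step 2).
- *Interrupted session, minute and reason:* no item comes close. The comorbidity rows name diseases, not session events.
- *Medical record and monitor records* (Sources of information): these may show some events, but nothing requires a search for them or makes the search the same in all arms.

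**2. Does a minute respiratory rate identify a brief apnea?** If the value is a one-minute count, the breaths left in the minute are RR × (60 − L)/60, where L is the pause in seconds. RR and L are assumptions, because the protocol gives neither and does not define apnea.

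| Pause L | RR 40 | RR 50 | RR 60 |
|---|---|---|---|
| 10 s | 33 | 42 | 50 |
| 20 s | 27 | 33 | 40 |
| 30 s | 20 | 25 | 30 |

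For example, 50 × 40/60 = 33. A 20-second pause in an infant breathing 60/min leaves 40, the same count as an undisturbed infant breathing 40/min. If the value is instead a spot reading at the minute mark, a pause starting at random covers the mark with probability L/60: 17%, 33% and 50% for 10, 20 and 30 s. Either way, a minute value does not mark the event.

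**3. How much of the session is observed?** The outcome definitions cover minutes 0 to 30. Description of interventions, Sources of information and Standardization of measurements stop at minute 10. If the shorter text were followed, (30 − 10)/30 = 67% of the session would have no planned reading.

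**4. Is an event plausible at this size?** With per-infant risk p (assumed; low values are included because recently unstable infants are excluded), P(at least one) = 1 − (1 − p)^n.

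| p | n = 15 | n = 30 |
|---|---|---|
| 1% | 14% | 26% |
| 2% | 26% | 45% |
| 5% | 54% | 79% |
| 10% | 79% | 96% |

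One unexplained interruption is 1/15 = 6.7% of an arm.

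**5. What could the counts show?** For zero events, the one-sided 95% upper limit is 1 − 0.05^(1/n): 1 − 0.05^(1/15) = 18.1% for one arm and 1 − 0.05^(1/30) = 9.5% for both music arms. Counts would describe the arms; they could not establish safety.

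**The case against.** The best reply has five parts.

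- **The data may exist anyway.** The Variable Matrix speaks of continuous measurement, vital signs come from unit monitor records, and clinical data come from the medical record. This stands to the extent that a reader might infer that the trial is unable to report these events at all, which the documents do not support. What is missing is prespecified capture that is uniform across arms. Whether stored monitor traces would resolve a short pause is not stated, and neither source is designed to hold the reason for stopping.
- **The safety sentence is not a trial claim.** A reader might take the favourable comparison in Ethical Considerations as something the trial sets out to show. It does not: the sentence rests on earlier studies, and no objective concerns safety. This stands in full.
- **The stated reason for the risk rating is already measured.** Heart rate, respiratory rate and saturation are recorded in all arms. This stands too and narrows the point to brief apnea and interruptions.
- **The event risks are assumed.** This is true. No figure in the protocol shows that an apnea is likely in infants who were stable for the previous 48 hours. Nor does the Background remark on noise show that music causes apnea: it concerns unpredictable sounds peaking at 120 dB, whereas the music is capped at 70 dB.
- **Withdrawal is a consent right, not a stopping rule.** This is correct: the protocol does not describe stopping sessions for instability. But a right to leave at any time makes an incomplete session foreseeable, whatever the reason.

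A descriptive table could be left to an analysis plan. The two data fields could not.

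**Conclusion.** The point holds in a limited form. The protocol rates itself above minimum risk but specifies no common way, across the live, pre-recorded and control arms, to record apnea or an interrupted session with its reason. Some events may be found afterwards in monitor or medical records. Brief apneas and reasons for stopping could not be recovered reliably or comparably by arm.

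The absence of the fields follows from reading the protocol and needs no assumption. The illustration that minute values hide short pauses rests on assumed breathing rates of 40 to 60/min, pauses of 10 to 30 s, and one count or spot value per minute. The chance of seeing any event rests on assumed risks of 1% to 10%.

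The consequence is moderate: safety reporting is weaker than it need be, while the primary heart rate comparison stands. Nothing here shows that the intervention is harmful.

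**What to change.** Add two fields to the form that the research assistant completes, identical in all three arms:

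1. **Apnea**, yes or no, using a definition that the neonatologists set before enrolment, since the protocol gives none.
2. **Session interrupted**, yes or no, with the minute and the reason (clinical, guardian's request, technical). In the control arm this refers to the matching observation period.

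Report both as descriptive counts by randomised arm, and keep interrupted infants in the arm to which they were randomised. Change the text that ends recording at minute 10, in Description of interventions, Sources of information and Standardization of measurements, to minute 0 to 30 so that it matches the outcome definitions.

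The cost is two fields, one agreed definition and a short table, handled by someone already at the cotside. Limits remain. The counts support no formal comparison (step 5). The recorder is not stated to be blinded, so apnea and reasons for stopping may be judged differently by arm. Under the outcome definitions, the stretch between the end of the session and the reading 30 minutes later is still not observed.
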